#### 2. AIMS

The study will enroll 252 MSM and 252 men who sex with women (MSW) into a double-blind, three-way randomized crossover trial with conditions of fitted, thin, and standard condoms. For the MSM arm of the trial we will assess outcomes based on anal sex, and for the MSW we will assess outcomes based on vaginal sex. We are conducting this trial with the objectives of (for Aims 1 and 2) establishing label indications for pleasure and patient preference for fitted condoms, (for Aim 3) establishing a label indication for anal sex for fitted, thin, and standard condoms, and (for Aim 4) establishing a label indication for decreased clinical failure of fitted condoms for anal sex.

**Aim 1.** To compare fitted condoms with standard condoms regarding levels of reported pleasure as determined by rating per condom use event.

**Hypothesis 1.** Fitted condoms will have higher pleasure ratings than standard condoms. **Hypothesis Rationale 1.** There is biological plausibility and published data indicating that condoms fitted to penile dimensions could improve perceptions of pleasure.

**Aim 2.** To compare fitted condoms with standard condoms regarding preference as determined by ranking of the two conditions at the study conclusion.

**Hypothesis 2.** More participants will prefer fitted condoms than standard condoms. **Hypothesis Rationale 2.** There is biological plausibility and published data indicating that condoms fitted to penile dimensions could improve perceptions of pleasure.

**Aim 3.** To assess for fitted, thin, and standard condoms the total clinical failure rate of each type of condom for anal sex among MSM relative to a cut-point to be determined by the United States Food and Drug Administration (FDA).

**Hypothesis 3.** All condom conditions will have clinical failure point estimates less than a cutpoint level of acceptable clinical failure, with the cut-point to be determined by the FDA. **Hypothesis Rationale 3.** Condoms are currently recommended for anal sex use for the prevention of STI and HIV by the U.S. Centers for Disease Control and Prevention (CDC), the United Nations, and the World Health Organization.

**Aim 4.** To compare fitted condoms with standard condoms regarding total clinical failure for anal sex among MSM.

**Hypothesis 4.** Fitted condoms will have a lower total clinical failure rate than standard condoms for anal sex among MSM.

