#### 3. STUDY OVERVIEW

# 3.0 Study Design

This study is a randomized crossover trial of 252 HIV-negative MSM and 252 HIV-negative MSW. Every participant in the trial will receive a batch of five fitted condoms, a batch of five thin condoms, and a batch of five standard condoms over a series of study visits. We will randomize the order in which fitted, thin, and standard condoms will be distributed. Eventlevel data based on a home coital log will be collected regarding pleasure and total clinical failure (Aims 1, 3 and 4), and data regarding overall condom preference (Aim 2) will be collected at the final study visit. All participants will complete an informed consent form (ICF) (uploaded to eIRB). Eligibility assessment will include HIV testing and symptomatic STI and acute HIV screening. The order in which study condoms will be received will be determined by permuted block randomization. Participants will be provided access to a mobile-optimized, web-based home coital log diary that is 21 U.S. Code of Federal Regulations (CFR) Part 11 compliant, in which participants will document each instance of study condom use as soon as possible following any vaginal or anal sex acts. Log entries will include assessment of pleasure and clinical failure, as well as other pertinent information such as substance use, lubricant, and any potential events including errors during application. Participants will be enrolled over a period of approximately 6-12 months, depending on the speed of recruitment. Each participant will be followed for six to twelve weeks after enrollment, depending on their use of study condoms in each two-week period between study visits (Figure 1). Participants will return for a follow-up visit two weeks after baseline. Participants will be given up to four weeks to use each study condom set; after 4 weeks with a set of condoms, participants will be automatically crossed over into the next study condition. If all condoms are used within the first two weeks, participants will crossover to the next randomized study condoms at that point (Figure 1). If participants do not use all study condoms in the first two weeks after the have been dispensed, participants will be given a second 2-week period to use the batch of condoms. Throughout the duration of study participation, coital logs will be completed.

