#### **6.3 Crossover Procedures**

There will be three crossover conditions during this study. Each participant will be given five of each study condom set and will have up to four weeks to use all five condoms.

If five coital log events are recorded by the end of the two-week follow-up visit for any crossover condition, participants will be crossed over to the next crossover condition or determined to have completed the study (after completing five coital log events for the third study condom set). If five coital log events are not recorded by the end of the two-week follow-up, participants will be given another two weeks to use the study condoms in that

[figure not shown]
crossover condition. At the four-week follow-up for the first two crossover conditions, participants will be automatically crossed over to the next crossover condition. Participants will be automatically completed in the study after four weeks on the third crossover condition. The crossover procedures and possible crossover condition combinations are shown in Figures 1 and 2 and Table 1.

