### Other areas of research interest:

- 1. To assess differences in total clinical failure between fitted, thin, and standard condoms.
- 2. To analyze aims regarding pleasure/preference and fitted condoms (Aims 1 and 2) restricted to participants who received fitted study condoms outside standard sizes of width, length, and both width and length.
- 3. To analyze aims regarding pleasure/preference (Aims 1 and 2) restricted to participants in the top and bottom deciles of self-reported penis size.
- 4. To explore correlates of condom failure (type of condom, SES, level of condom experience, partner genital piercings).
- 5. To compare history of experiencing condom slippage and breakage with slippage and breakage experienced in the study period.
- 6. To perform visual analysis of condom breaks, and correlates of breakage types.
- 7. To compare a baseline measure of perceptions of pleasure during condom use to event-level pleasure reported in the coital logs.
- 8. To compare previous measures of pleasure (history of pleasure using condoms) to pleasure prospectively reported during the study.
- 9. To assess whether there were differential changes in pleasure for certain individuals: those with history of erectile dysfunction or sexual performance issues; participants with certain penile dimensions; MSM vs. MSW.
- 10. To understand the clinical failure rate when a single condom is used for multiple types of sex (oral, anal, and/or vaginal), and correlates of this type of condom usage.
- 11. To compare history of erectile dysfunction and sexual performance issues to consistency of condom use.
- 12. To compare measures of pleasure between MSM and MSW enrolled in the study.
- 13. To understand willingness and acceptability to use condoms, and reasons why participants do not use condoms through a comparison willingness at baseline to willingness at the end of the study period.

- 14. To understand the stability of condom preferences over time (prior to beginning the third crossover condition and at the end of the study).
- 15. To assess effect modification of study arm (i.e., MSM vs. MSW) on the relationship between study condition and outcome measure (i.e., pleasure or preference) for Aims 1 and 2.

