Aim 1 involves the pair-wise comparison of pleasure scores between fitted and standard condoms. A linear mixed effects model with random effects for person and including arm, condom type, cross-over period, and an arm*condom type interaction term will be conducted to account for repeated measures within participants (i.e. the crossover design) and for repeated measures on coital acts within each of the three conditions. Model-based estimates and confidence intervals of the difference in pleasure score will be used to compare fitted and standard condoms. Additional control for participant-, partner-, and event-level correlates of pleasure in the above model will be considered in secondary analyses. The primary analysis of Aim 2 will be conducted at the participant-level, using binary preference responses for comparison of fitted and standard condoms, collected at the final study visit (Table 1). For Aim 2, we will assess whether a majority of participants preferred fitted over standard condoms using a logistic regression model with preference as the outcome with arm and cross-over period as covariates. A confidence interval around the estimated probability of fitted condom preference will be computed.

A descriptive assessment for Aim 3 will consist of calculating the per-anal sex act clinical failure proportion for the 3 condom conditions by dividing the number of total clinical failures by the total number of acts contributed for each condom type by participants in the MSM arm of the

study. We will assess whether the proportion of failure for each condom type is below the threshold value that is to be determined by FDA. In order to adjust for study design, failure will also be assessed with a logistic mixed effects model with random effects for person with arm, condom type, cross-over period, and an arm*condom type interaction term.

For Aim 4, we will use the logistic mixed model described in Aim 3 to assess the odds of failure for fitted versus standard condoms within the MSM arm. Instances of anal sex among MSW will not be included in primary analyses because anal sex events occur frequently at the lifetime level for MSW, but infrequently at monthly- and even yearly- levels,[1] This indicates lower levels of experience with this type of sex for many MSW, an issue that could introduce bias into study outcome assessment.

Measures

Coital log measures

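### The Aim 1 mixed model names a random effect for person only, so its interval is too narrow if acts within one condom batch are correlated

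*SAP*

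**What the plan says.** The SAP, Data analysis, describes the Aim 1 model as "A linear mixed effects model with random effects for person and including arm, condom type, cross-over period" and an arm-by-condom-type interaction. It says the model is there to account for repeated measures within participants and also "for repeated measures on coital acts within each of the three conditions". Inference is model-based: "Model-based estimates and confidence intervals of the difference in pleasure score will be used to compare fitted and standard condoms". For Aims 3 and 4 it uses the same structure, a "logistic mixed effects model with random effects for person with arm, condom type, cross-over period" and the same interaction.

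Person is the only random grouping named. Neither document mentions a participant-by-condition term, a random condom-type slope, a residual correlation structure or a robust variance. Protocol section 9.4 lists outcome measures but gives no model.

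The data come in batches. Protocol section 6.3: "Each participant will be given five of each study condom set and will have up to four weeks to use all five condoms". Section 3.0: "after 4 weeks with a set of condoms, participants will be automatically crossed over into the next study condition". The outcome is one pleasure score per act.

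**The concern.** There are three levels: acts within batches, and batches within men. Condom type varies at the batch level. A random intercept for person makes acts independent given the person, so it treats five acts from one batch as five independent replicates of that condom type. Anything else the acts in a batch share is left out, such as the partner or circumstances of those weeks, or a man's own response to that condom type. If such sharing exists, the model counts more information on the fitted-versus-standard difference than there is.

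The SAP's sentence claims to cover the acts-within-condition level, but the only random term it names does not do so. Because the interval is model-based, it is only as good as the stated covariance. Protocol section 2 gives the purpose of Aims 1 and 2 as "establishing label indications for pleasure and patient preference for fitted condoms", so a false positive on pleasure would bear on a label claim.

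**Working it through.** **The plan's own figures.** Retention reproduces: 504 × 0.80 = 403.2. The Aim 1 power of more than 99% cannot be reproduced, because no effect size, SD or correlation is given. The SAP gives alpha 0.05 without stating sidedness; the main results below take it as two-sided.

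**Inputs.** From the documents: K = 3 conditions, m up to 5 acts per batch, n = 403 completers. Assumed: rho, the share of within-person variance common to acts in one batch, over 0 to 0.30. Within-person variance is set to 1, so the batch variance is rho and the act-level variance is 1 − rho.

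**Formulas, five acts in every batch (per person).**
- True variance of the fitted-minus-standard difference: 2(rho + (1 − rho)/5).
- The person-only model pools all within-person variation into one residual on Km − 1 = 14 degrees of freedom: s² = [2((1 − rho) + 5·rho) + 12(1 − rho)]/14. It reports 2s²/5.
- Actual two-sided error: P(|Z| > 1.96/R), where R is the true SE divided by the reported SE.

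Example, rho = 0.10: true variance 2(0.10 + 0.18) = 0.56; s² = (2.8 + 10.8)/14 = 0.971; reported variance 0.389; ratio 1.44; R = 1.20; 1.96/1.20 = 1.63; error 10.3%.

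| rho | variance ratio | R | actual error |
|---|---|---|---|
| 0 | 1.00 | 1.00 | 5.0% |
| 0.05 | 1.22 | 1.10 | 7.6% |
| 0.10 | 1.44 | 1.20 | 10.3% |
| 0.20 | 1.91 | 1.38 | 15.6% |
| 0.30 | 2.41 | 1.55 | 20.6% |

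The between-person variance cancels and does not affect R.

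**Fewer acts per batch.** The same algebra with two acts gives 5.7, 6.4, 8.0 and 9.6% at rho 0.05, 0.10, 0.20 and 0.30. With one act per batch there is no effect.

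**Simulation.** 4,000 null trials per setting, 403 men, REML person intercept, fixed arm, condom type, period and arm-by-condom-type; Monte Carlo SE 0.3 to 0.6 points. Person-only rejection rates:

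| rho | five acts | 60% of batches with five, rest 1–4 | 1–5 acts |
|---|---|---|---|
| 0 | 4.8% | 5.1% | 4.9% |
| 0.05 | 8.1% | 7.9% | 6.4% |
| 0.10 | 9.7% | 9.9% | 9.1% |
| 0.20 | 16.1% | 13.6% | 11.8% |
| 0.30 | 20.6% | 18.7% | 15.2% |

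At rho 0.20 the reported SE is 28% too small with five acts and 19% too small with one to five acts. Participant-clustered SEs gave 4.9 to 5.9% in all 15 settings. In a separate simulation of 2,000 trials per setting, a participant-by-condition random effect gave 4.2 to 5.3% for rho 0.05 to 0.30.

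**Aim 4.** 1,500 null trials per setting, 252 × 0.8 = 202 MSM, five acts, person SD 1.0 on the logit scale (assumed). With 6.5% failure, between the 6.3% and 6.9% in the protocol's Introduction, person-only error was 4.7, 7.0, 7.9, 8.7 and 14.7% for batch SD 0, 0.5, 0.7, 1.0 and 1.5. With 2% failure (assumed) it was 4.7, 5.8, 7.5, 6.6 and 9.7%. Monte Carlo SE was 0.5 to 0.9 points. Clustered SEs gave 4.9 to 6.6%.

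**The case against.** The strongest reply is that this is under-specification, not a shown error. The sentence states an intent to cover acts within each condition, and the plural for the random effects could include a person-level condom-type effect. That may be what was meant, but the SAP does not say it, and an analyst following the text would fit a person intercept.

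Second, no document establishes rho above zero. The protocol's other research interests include "To assess whether there were differential changes in pleasure for certain individuals", but that item is exploratory and refers to measured characteristics: sexual-performance history, penile dimensions, and MSM versus MSW. The last is already in the model through the interaction. Also, if fitted and standard condoms differ for no man, different responses to them cannot inflate the error; that source operates only when the average difference is zero but individual differences are not. These points stand, so the size is unknown. They do not justify building zero into the primary model, and shared circumstances within a batch remain a possible source.

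Third, the SAP plans secondary analyses adjusting for partner- and event-level correlates. These may absorb part of the correlation but do not change the primary interval.

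Fourth, five acts in every batch is the worst case: entry requires only one act in the past four weeks, and crossover is forced after four weeks. Fewer acts reduce the inflation, as shown above. Sidedness also matters. The Aim 2 range of 0.56 to 0.57 matches a one-sided 0.05 test (0.562 and 0.573) rather than a two-sided one (0.570 and 0.580). If Aim 1 were also one-sided, the five-act errors would be 6.8, 8.5, 11.7 and 14.4%. These points lower the size but leave the direction unchanged.

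Finally, the Aim 4 effect is weak. At 2% failure and batch SD up to 1.0 it is hard to distinguish from the clustered-SE results.

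**Conclusion.** The concern holds as a conditional statement. As written, the Aim 1 model gives too narrow a fitted-versus-standard interval whenever rho is above zero and batches hold more than one act; at rho zero it is valid. For rho 0.05 to 0.30, two-sided error at nominal 5% runs from 7.6 to 20.6% with five acts per batch, 6.4 to 15.2% with one to five acts, and 5.7 to 9.6% with two. These figures rest on assumed values of rho, so confidence in the size is medium.

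The exposure is in error rate and coverage; the power claim is not undermined. The logistic model for Aims 3 and 4 has the same gap with a much smaller effect. Aim 2 and the descriptive Aim 3 proportions do not use these models. The documents do not show what model was actually fitted. This should be fixed, because Aim 1 supports a label claim and the correction is simple.

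**What to change.** In the Aim 1 model, state random intercepts for participant and for participant-by-condom-type. The latter is the same as participant-by-period here, since each man receives each type in one period. Alternatively, keep the person intercept and use participant-clustered robust standard errors. Apply the same to the logistic model for Aims 3 and 4, with participant-clustered robust standard errors as the stated fallback, since the extra term may not converge at low failure rates. If GEE is used there, say that the odds ratio becomes population-averaged rather than conditional on the person.

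The cost is SAP wording and one random term; no new data are needed. With five acts per batch the Aim 1 interval widens by factors of 1.10, 1.20, 1.38 and 1.55 at rho 0.05, 0.10, 0.20 and 0.30, and does not change at rho zero. The difference detectable with 99% power at two-sided 0.05 is (1.96 + 2.33) × √[2(rho + (1 − rho)/5)/403]. That is 0.135 within-person SD at rho 0, 0.16 at rho 0.10 and 0.18 at rho 0.20.
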